Participants (N = 40) will be primarily recruited through Western Wayne Family Health Center's clinic in Inkster, Michigan.

**Description of Study
Intervention/Experimental
Manipulation:**

The STEP-UP chronic pain self-management intervention (Support, Training, and Education for Pain Self-Management – Using Podcasts) will feature an educational podcast series teaching core pain self-management skills. Podcasts will be supplemented by sessions with a Community Health Worker taking place at designated times over a 7-week period. The Community Health Worker will guide participants in a modified Patient Priorities of Care (PPC) approach to help them identify their values and priorities and develop goals that reflect these..

Study Duration*:

One year

Participant Duration:

Eight weeks

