2 OBJECTIVES & ENDPOINTS

OBJECTIVES	ENDPOINTS	JUSTIFICATION FOR ENDPOINTS
Primary		
To determine if participating in the STEP-UP intervention leads to decreased pain interference with daily functioning.	PROMIS Pain Interference 6a scale is the primary endpoint (pain interference is assessed at baseline, and 8 weeks from baseline). A 2.5 point difference in T-score is considered clinically significant.	Pain interference is a patient-centered outcome that indicates pain's impact on valued and necessary activities. This intervention teaches skills such as goal setting to gradually increase engagement in daily activities.
Secondary		
To determine if participating in the STEP-UP intervention leads to greater improvement in Global Impression of Change in Pain and Functioning.	Patient Global Perception of Change since baseline will be assessed at 8 weeks. Participants will be asked about pain and functioning in separate items.	“Global impression of change” variables capture participants’ subjective perceptions of intervention benefit.

To assess participant engagement in the intervention.	Number of sessions (out of 7) completed at 8 weeks from baseline.	Given the novel nature of this intervention and the barriers that many participants may experience to engagement, it is important to assess whether the intervention as designed yields acceptable engagement levels.
To assess participant satisfaction with the intervention.	Items ask about overall satisfaction with the program, e.g., whether participation increased understanding of pain management (1= Strongly Disagree to 5= Strongly Agree). A higher score indicates higher patient satisfaction.	These items will facilitate understanding of the intervention's acceptability in the priority population as well as highlight potential areas for improvement prior to a larger trial or another future iteration of the intervention.

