3 STUDY DESIGN

3.1 Study Design

- NIH Behavioral Intervention Stage 1 randomized pilot trial to examine the acceptability and preliminary effects of the STEP-UP program on pain interference among older adults with chronic pain compared to a control group.
- Participants will be allocated into the two study arms in a 1:1 ratio by block randomization with mixed block sizes.

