7 STUDY PROCEDURES

7.1 Schedule of Activities

Activity	Weeks									
	Pre	0	1	2	3	4	5	6	7	8
Eligibility Screening	X									
Consent Process	X									
Randomization	X									
Demographics		X								
Chronic conditions and overall health		X								
Pain Interference (PROMIS-43 6-item scale)		X								X
PROMIS-29 +2 ^{14,15} (except Pain Interference subscale)		X								X
Pain Intensity (Numerical Rating Scale)		X								X
Pain Self-Efficacy Questionnaire		X								X
Pain Medication Use		X								X
Communication with Provider		X								X
Chronic Pain Acceptance		X								X
Physical Activity		X								X
Fear of Movement		X								X
Patient Activation Measure		X								X
Survey of Pain Attitudes (SOPA) - Control subscale		X								X
Pain Catastrophizing Scale		X								X
Life Control Scale		X								X
PROMIS Meaning and Purpose (4-item)		X								X
Global impression of change in pain, functioning, quality of life, and use of pain medication										X
STEP-UP Program Evaluation Questions (intervention group only; both close- and open-ended)										X

STEP-UP: CHW sessions (intervention group only)				X	X	X	X	X	X		
---	--	--	--	---	---	---	---	---	---	--	--

Notes:

*Shaded rows represent measures on the telephone data collection surveys (at baseline and/or 8 weeks).

**Primary and secondary outcomes are bolded.

***Allowable assessment windows: Participants need to complete the assessment within one month of the follow-up due date to be counted as non-missing.

****If participant does not start intervention within one month of baseline assessment, they will be withdrawn from the study by the study team. If a participant drops out of the intervention, they will be invited to complete the surveys if they want to (intent to treat) or they can withdraw from the study.

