11.2.2 Primary & Secondary Endpoints

We will calculate baseline descriptive statistics and compare groups using independent-sample t-tests for continuous variables and chi-squared tests for categorical variables. We will assess psychometrics of scales used (e.g., internal consistency reliability and concurrent validity). We will convert the PROMIS 6-item Pain Interference subscale score to T-scores (a standardized score with a mean of 50 and SD of 10) by summing the scales and using the conversion tables provided at HealthMeasures.net.

To assess the effect of being in the intervention group, we will use a univariate analysis of variance model for continuous primary and secondary outcomes. The dependent variable in each model will be the value of the outcome at 8-week follow-up; the independent factor will be treatment group (intervention vs. control), with the baseline value of the outcome as a covariate.

Effect size will be indicated by partial eta squared for the treatment group variable. In order to assess the potential clinical relevance of the intervention, we will use chi-squared tests to compare the percentage of participants in each treatment condition who achieved the Minimally Important Difference (MID) of ≥ 3 T-score points in PROMIS pain interference.

We will repeat this analysis with the secondary outcomes: Global Impression of Change in Pain and Functioning. Transformations for non-normality of outcomes will be performed as indicated.

We will also assess the moderating effect of selected variables such as sex, age, baseline pain intensity, and degree of program engagement. Moderation analyses will use standard approaches to evaluate interactions between these covariates and treatment group.

For patient engagement, the secondary outcome indicating feasibility that is composed of: 1) number of sessions completed out of 7; and 2) participant satisfaction on a 5-point Likert scale, we will calculate descriptive statistics. We will also explore differences by age group (under 65/65+) as well as gender. As an exploratory analysis, we will investigate whether satisfaction differs according to whether or not participants achieved the MID on the primary outcome of pain interference.

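### The exploratory satisfaction analysis relates satisfaction to benefit only through a yes/no split at 3 T-score points, which discards at least about 36% of the information in the change score among at most about 20 people.

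*Combined protocol and SAP*

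**What the plan says.** - **The analysis.** Section 11.2.2 states, as an exploratory step, that "we will investigate whether satisfaction differs according to whether or not participants achieved the MID on the primary outcome of pain interference". It names no test, significance level or effect measure for this step.
- **The cut.** The same section uses a "Minimally Important Difference (MID) of ≥ 3 T-score points in PROMIS pain interference". It introduces this cut for comparing the arms and then reuses it to label individuals here.
- **Who contributes.** Section 7.1 lists "STEP-UP Program Evaluation Questions (intervention group only; both close- and open-ended". Section 6.3 adds that controls who take up the programme later complete no further surveys. The Protocol Summary gives "Participants (N = 40) will be primarily recruited", and section 3.1 says "Participants will be allocated into the two study arms in a 1:1 ratio".
- **The scale.** Section 11.2.2 describes the T-score as "a standardized score with a mean of 50 and SD of 10" and says that internal consistency will be assessed in the trial. It states no reliability value. Satisfaction is rated on a 5-point Likert scale.
- **Not planned.** No analysis relates satisfaction to the continuous T-score or its change, although section 7.1 has pain interference measured at baseline and at 8 weeks.

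**The concern.** Splitting at 3 points treats a participant who improved by 3 points like one who improved by 15, and separates a 2.9-point change from a 3.1-point change. With about 20 people, that loss matters. Each label also rests on one person's difference between two administrations of a six-item form, so measurement error will move some people across the cut. Both effects make a real link between benefit and satisfaction harder to see.

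What is at stake is modest. Section 2 says the satisfaction items are meant to show acceptability and point to improvements before a larger trial. This is the only planned analysis that sets satisfaction against benefit, and a diluted comparison would inform that purpose poorly.

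**Working it through.** The plan gives no power or precision figure for this analysis, so there is none to reproduce.

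**1. Number of people.** 40 participants at 1:1 gives 40 / 2 = 20 in the intervention arm. No dropout rate is stated, so the analysable number may be lower.

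**2. Loss from the cut.** This step needs no value for reliability. For a normal variable cut so that a share p falls in one group, the share of information kept is φ(z)² / [p(1 − p)], where z is the normal quantile for p.

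| Split | φ(z) | Information kept | Equivalent n of 20 |
|---|---|---|---|
| 50/50 | 0.399 | 0.159 / 0.25 = 0.64 | 12.7 |
| 30/70 | 0.348 | 0.121 / 0.21 = 0.58 | 11.5 |
| 20/80 | 0.280 | 0.078 / 0.16 = 0.49 | 9.8 |

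The even split is the best case, so the loss is at least 1 − 0.64 = 36%.

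**3. Noise in the individual labels.** This step rests on assumptions: sample SD 6 to 10 and reliability 0.80 to 0.95. The standard error of one person's change is SE = SD × √(1 − reliability) × √2. For example, 10 × √0.10 × √2 = 4.5 points.

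Assume also that true improvement is normal with mean 3 and SD 4. The mean then sits on the cut, and the probability that the observed label differs from the true one is arctan(SE / 4) / π.

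| SD | Reliability | SE of change | Misclassified |
|---|---|---|---|
| 6 | 0.80 | 3.8 | 24% |
| 6 | 0.90 | 2.7 | 19% |
| 6 | 0.95 | 1.9 | 14% |
| 8 | 0.80 | 5.1 | 29% |
| 8 | 0.90 | 3.6 | 23% |
| 8 | 0.95 | 2.5 | 18% |
| 10 | 0.80 | 6.3 | 32% |
| 10 | 0.90 | 4.5 | 27% |
| 10 | 0.95 | 3.2 | 21% |

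The range is 14% to 32%. Of 20 people, that is 0.14 × 20 = 2.8 to 0.32 × 20 = 6.4, or about 3 to 6.

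**4. Sensitivity.**
- A mean on the cut is the worst case for the mean. With mean 0 or 6 and the other assumptions unchanged, the range is 11% to 28%.
- The spread matters too. With standard errors of measurement (SEM, for a single score) from 1.5 to 4.47, mean true change 0, 3 or 5, and SD of true change 3, 5 or 7, the range is 9% to 36%, about 2 to 7 of 20.

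**5. What the continuous score recovers.** This is a simulated illustration with n = 20, true change with mean 3 and SD 5, a correlation of 0.5 between satisfaction and true change, and a two-sided 5% test. All of these are assumed, and satisfaction is treated as continuous.

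| SEM of a single score | Power, continuous change | Power, split at 3 |
|---|---|---|
| 0 | 0.64 | 0.43 |
| 2.24 | 0.48 | 0.32 |
| 3.16 | 0.38 | 0.25 |

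Reading across a row shows what the cut costs. Reading down the continuous column shows the attenuation from measurement error, which the continuous analysis does not remove.

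**The case against.** The strongest reply is that the analysis is labelled exploratory, names no test, and belongs to a pilot that section 11.1 declares unpowered. No decision depends on it, and reusing the responder definition applied to the arms keeps the report consistent. All of that stands. It limits the importance of the point and is a good reason to keep the split as description. It does not justify discarding information already collected, and an unpowered analysis is better served by an estimate with an interval.

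Four stronger readings are tempting, and the documents do not support them.

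- **That many participants will certainly be mislabelled.** This depends on reliability and on the spread of true change, and the documents give neither.
- **That 3 points is smaller than one standard error of an individual's change.** The SD of 10 describes the reference metric, not this sample, which is restricted to high-impact chronic pain. In three of the nine cells in the first misclassification table the standard error is below 3 points (1.9, 2.5 and 2.7).
- **That using the continuous score cures the measurement problem.** It recovers only the loss from the cut. In the illustration a real link would still often be missed.
- **That nothing else links acceptability to benefit.** Section 11.2.2 lists degree of engagement as a moderator, and section 11.2.3 plans sensitivity analyses by session completion. The gap is specific to satisfaction.

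The power figures also presuppose a significance test that the plan does not specify here, and they do not model the 5-point scale. They show direction only.

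**Conclusion.** The point holds as a minor, inexpensive improvement. The loss of at least 36% of the information, rising to 51% at a 20/80 split, needs only approximate normality of the change score. It leaves 20 people doing the work of about 10 to 13. Misclassification of 14% to 32% is conditional on the stated assumptions and should be quoted only with them. The efficiency figures are large-sample approximations and are indicative at this sample size. No primary or secondary conclusion changes.

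**What to change.** In section 11.2.2, make the main satisfaction-benefit analysis the association between satisfaction and the continuous Pain Interference T-score in the intervention arm, reported as an estimate with a 95% confidence interval. Two forms are suitable:

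- a rank correlation between satisfaction and change in T-score, which suits the 5-point scale; or
- a regression of satisfaction on the 8-week T-score with the baseline T-score as covariate.

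Keep the MID split as a descriptive table, and note there that a 3-point change does not by itself establish that an individual improved. Report the reliability observed in the trial beside it.

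The cost is about one sentence, with no new data, visits or participants. The main result becomes a correlation or slope instead of a two-group comparison. A side benefit is that it no longer depends on which threshold applies: section 2 says "A 2.5 point difference in T-score is considered clinically significant", while section 11.2.2 uses 3 points. Those two statements should be reconciled separately, because the descriptive table still depends on one of them.

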11.2.3 Other Pre-specified Analyses

To explore potential mechanisms, we will examine the association between: 1) participation in the intervention and the hypothesized composite mediator, Perceived Control Over Pain, as well as each of the 4 component scales (Survey of Pain Attitudes Control subscale, Pain Catastrophizing Scale, Life Control scale, and PROMIS Meaning and Purpose); and 2) between mediators and outcomes. Positive correlations in both cases will provide evidence for a potential mediating effect.

Following intent-to-treat principles, we will include all participants randomized to the intervention group, with sensitivity analyses assessing whether different levels of participant engagement (i.e., session completion) impact results.

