11.2.1	General Approach	28
11.2.2	Primary & Secondary Endpoints	29
11.2.3	Other Pre-specified Analyses	29
12	Interim Analysis	30
13	Publications	30
14	protocol amendment history	30

STATEMENT OF COMPLIANCE

The trial will be carried out in accordance with International Conference on Harmonisation Good Clinical Practice (ICH GCP) and the following:

- United States (US) Code of Federal Regulations (CFR) applicable to clinical studies (45 CFR Part 46, 21 CFR Part 50, 21 CFR Part 56, 21 CFR Part 312, and/or 21 CFR Part 812)

National Institutes of Health (NIH)-funded investigators and clinical trial site staff who are responsible for the conduct, management, or oversight of NIH-funded clinical trials have

completed Human Subjects Protection and ICH GCP Training.

The protocol, informed consent form(s), recruitment materials, and all participant materials will be submitted to the Institutional Review Board (IRB) for review and approval. Approval of both the protocol and the consent form must be obtained before any participant is enrolled. Any amendment to the protocol will require review and approval by the IRB before the changes are implemented to the study. In addition, all changes to the consent form will be IRB-approved; a determination will be made regarding whether a new consent needs to be obtained from participants who provided consent, using a previously approved consent form.

PROTOCOL SUMMARY^{CT.GOV}

Title:

A pilot and feasibility study of a chronic pain self-management intervention for older adults incorporating podcasts and patient priorities.

Study Description:

This randomized pilot trial tests the feasibility of a community health worker (CHW)-delivered chronic pain self-management intervention for older adults ("STEP-UP"; Support, Training, and Education for Pain Self-Management – Using Podcasts) in a primary care setting.

Objectives*:

We will conduct a randomized (waitlist) pilot trial (n=40) in a Federally Qualified Health Center.

Endpoints*:

Primary Endpoint: Improvement in pain interference at 8 weeks (post-program)
Secondary Endpoints: physical functioning and global impression of change, and participant engagement and satisfaction (secondary outcomes) at 8 weeks

Study Population:

We will recruit 40 adults from a FQHC who are age 50+ with high-impact chronic pain.

Phase* or Stage:

Stage 1 (Behavioral Stage Model) Pilot Trial

**Description of Sites/Facilities
Enrolling Participants:**

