11 STATISTICAL CONSIDERATIONS

11.1 Sample Size

This pilot study is not powered to determine the statistical significance of effects.

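### The arm-to-mediator step in Section 11.2.3 names no time point or model and makes no use of the mediators' baseline values, although these are collected

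*Combined protocol and SAP*

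**What the plan says.** Section 11.2.3 sets out the mechanism analysis in two steps. The first examines the association between "participation in the intervention and the hypothesized composite mediator, Perceived Control Over Pain, as well as each of the 4 component scales". The second relates mediators to outcomes. The criterion for both is: "Positive correlations in both cases will provide evidence for a potential mediating effect". The section does not say at which visit the mediator is taken, whether its level or its change is used, which model is fitted, or whether any covariate enters.

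Section 11.2.2 is more specific for outcomes: "we will use a univariate analysis of variance model for continuous primary and secondary outcomes", "with the baseline value of the outcome as a covariate". The mediators are neither primary nor secondary outcomes, so this rule does not reach them.

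The schedule in 7.1 marks "Survey of Pain Attitudes (SOPA) - Control subscale" and the other three component scales (Pain Catastrophizing, Life Control, PROMIS Meaning and Purpose) at week 0 and week 8. The baseline values will therefore be in the database.

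On size and allocation, the Protocol Summary states: "We will conduct a randomized (waitlist) pilot trial (n=40) in a Federally Qualified Health Center". Section 3.1 adds: "Participants will be allocated into the two study arms in a 1:1 ratio by block randomization with mixed block sizes". No stratification is described. Section 11.1 states: "This pilot study is not powered to determine the statistical significance of effects".

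**The concern.** A correlation between a two-group variable and a score is, in effect, an unadjusted comparison of two means. At 20 per arm, chance differences in baseline catastrophizing or perceived control can be sizeable, and part of any such difference persists at week 8. An analysis that leaves baseline out can show that remnant as a program effect on the mediator, or let it mask a real one. The criterion turns on the sign of the correlation, so a modest shift can change the conclusion. The covariate that would remove this noise is already collected, and the plan already uses the same device for its outcomes.

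The point is confined to the precision of the arm-to-mediator estimate and its exposure to chance imbalance. It does not address the mediator-to-outcome step, the scoring direction of the scales, or how strong an association should count as evidence.

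**Working it through.** The documents give no power, effect size, standard deviation or precision figure for any analysis, so there is nothing to reproduce. The check sizes the gap in units of the mediator's standard deviation.

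Inputs from the documents:
- N = 40 (Protocol Summary) at 1:1 (3.1), so n = 20 per arm.
- Mediator scales at weeks 0 and 8 (7.1). Week 8 is the only post-baseline measurement.

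Assumptions not in the documents:
- Participation means assigned arm, the week-8 level is analysed, and all 40 participants contribute.
- The baseline-to-week-8 correlation r is 0.3, 0.5 or 0.7.
- For the wrong-sign calculation, the true arm effect is 0.3 SD.

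**Chance imbalance.** The SD of the baseline arm difference is sqrt(2/20) = 0.316. The probability that it exceeds 0.3 SD in either direction is 2 × (1 − Φ(0.3/0.316)) = 0.34.

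**Carry-over.** A fraction r of the imbalance enters the unadjusted week-8 difference. A 0.3 SD imbalance shifts it by 0.3 × r.

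**Precision.** Unadjusted SE = sqrt(2/20) = 0.316. Baseline-adjusted SE = 0.316 × sqrt(1 − r²) × sqrt(1 + 1/(N − 4)). The last factor, sqrt(37/36), is the small-sample price of estimating the slope. Adjustment helps only if (1 − r²) × 37/36 < 1, which means r² > 1/37, or r above about 0.16.

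**Wrong sign at a true 0.3 SD effect.** Φ(−0.3/SE). Unadjusted, this is Φ(−0.949) = 17%.

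| r | Shift from 0.3 SD imbalance | Adjusted SE | Variance ratio to unadjusted | Equivalent unadjusted n per arm | Wrong sign, adjusted |
|---|---|---|---|---|---|
| 0.3 | 0.09 | 0.306 | 0.94 | 21 | about 16% |
| 0.5 | 0.15 | 0.278 | 0.77 | 26 | about 14% |
| 0.7 | 0.21 | 0.229 | 0.52 | 38 | about 9.5% |

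A simulation of 40,000 trials at 20 per arm agrees. The unadjusted estimate had mean about 0 under no effect. Its slope on the baseline imbalance was 0.30, 0.50 and 0.70 at the three values of r, and about 0 after adjustment. The SD of the adjusted estimate was 0.306, 0.276 and 0.229.

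**If a change score is what is meant.** The text would also allow this. Its SE is 0.316 × sqrt(2(1 − r)) = 0.374, 0.316 and 0.245 at r = 0.3, 0.5 and 0.7. Each is larger than the adjusted SE. A change score also carries imbalance over, with slope r − 1, so in the opposite direction.

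**The case against.** The strongest reply is that the plan is silent rather than wrong. A reader might infer from 11.2.3 that the sponsor has chosen an unadjusted week-8 comparison by arm. The documents do not say so: time point, level versus change, and the meaning of participation are all left open. A change score would use the baseline, and at r = 0.7 its SE of 0.245 already secures most of the gain over 0.316. This stands. The defect is that the analysis is unspecified, although the word correlations in the criterion leans towards an unadjusted two-variable analysis. The silence does not remove the point, because adjustment is more precise than either alternative at all three values of r in the table.

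A reader might also infer that the mediators are the only twice-measured scales compared between arms without a baseline covariate. They are not. The chi-squared test in 11.2.2 of the share reaching the minimally important difference in pain interference has none either, and uses baseline only through change.

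Third, chance imbalance is not systematic bias. Averaged over randomisations the unadjusted estimate is correct, and its standard error already reflects the imbalance. What remains is error within the single trial that is run, together with avoidable imprecision. The baseline group comparisons in 11.2.2 could show an imbalance but would not correct for it. The covariate screening in 11.2.1 is general and tied to the primary analyses.

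Finally, the analysis is exploratory in a pilot that disclaims power, and its conclusion is only a potential mediating effect. This stands too, and limits how much weight the point can bear.

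**Conclusion.** The point holds as a minor one: 11.2.3 leaves the arm-to-mediator step without a time point, a model or any use of baseline values that the trial collects. The benefit of adjustment depends on r, which the documents do not give. The variance reduction is about 6% at r = 0.3, 23% at r = 0.5 and 48% at r = 0.7, and there is none below about r = 0.16. A claim of a large gain would rest on the higher values alone. The figures assume assigned arm, week-8 levels and 20 analysed per arm.

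The step stays imprecise even when adjusted: the 95% half-width (1.96 × SE) is about 0.54 SD at r = 0.5 and 0.45 SD at r = 0.7, against 0.62 SD unadjusted. No primary, secondary or safety result is affected.

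**What to change.** In 11.2.3, state that the week-8 score of the composite and of each of the four scales will be modelled on randomised arm with that score's own baseline value as covariate, as 11.2.2 does for outcomes. Report each adjusted difference with a 95% confidence interval.

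Two consequential edits are needed. The composite must be scored in the same way at weeks 0 and 8, and that scoring should be written down, because the documents do not define it. The step-1 criterion should become an adjusted arm difference in the hypothesised direction, because a positive correlation would no longer be the quantity estimated.

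The cost is a few sentences, five short models on data already collected, and one degree of freedom per model. No new data are required.

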The intervention and control conditions will be described as follows. Individuals in the intervention group will meet with a community health worker for a 1-1.5 hour orientation session (typically in person but may be virtual in special cases described in Section 6.2) to get oriented to the program, receive a hard-copy workbook, and engage in a values-clarification and goal-setting exercise. Participants will then be asked to listen to one podcast episode per week for five weeks, each presenting a new pain self-management skill. Podcasts will be made available by both website and an IVR system. Each week, participants will receive a reminder text, voicemail, and/or brief telephone call from the CHW encouraging them to listen to that week's podcast episode, complete corresponding tasks as described in the workbook, and continue to work on their goal. After completing the follow-up telephone survey at 2 months from baseline (see below), individuals in the control group will be invited to take part in the intervention.

Participants in both groups will be asked to complete two data collection telephone interviews (at baseline and 8 weeks from baseline), each of approximately 45 minutes in length.

Informed consent procedures: If an eligible individual expresses interest in participating, they will be asked to verbally consent over the phone, either right away or on a subsequent call, according to participant preference and whether the participant completes the eligibility screener in-person or over the phone as mentioned earlier in Section 5.4. Participants will have the option to have a copy of the consent document mailed or emailed to them to review beforehand, or they can choose to complete the verbal consent first and have a copy of the consent document mailed or emailed to them afterward. The consent document will be mailed in a packet that also contains survey scale options for the initial, baseline survey. These are the response options for each of the survey items so the participant can more easily follow along on the telephone.

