6 STUDY INTERVENTIONS

Participants will be randomized to one of two study arms in a 1:1 ratio: Arm 1 will receive the STEP-UP intervention and Arm 2 will be in the control group and will be waitlisted to be invited to receive the intervention.

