7.2 Description of Activities

- *Telephone data collection surveys* – participants will complete the validated measures tested as outcomes or mediators listed above as well as other measures to help characterize health and functional status, quality of life, and satisfaction with the intervention, at baseline and/or 8 weeks from baseline. Participants will be sent response options for each of the survey scales prior to their scheduled telephone survey appointment so they can see the response options and follow along. If participants do not have the survey scales, they can either reschedule or continue with the survey if they prefer (staff will read responses for each question/item on the survey).
- *Randomization* – occurs after a participant completes their baseline telephone survey.
- *STEP-UP Program (Intervention)* – See Table in Section 6.2 for details of intervention activities and flow..

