11.2 Data Analyses

11.2.1 General Approach

We will collect outcome data at two time points: baseline and 8 weeks from baseline (post-program, for those in the intervention group). All quantitative process and outcome data will be collected in REDCap. Descriptive statistics will be used to summarize background variables for the overall sample and by treatment group. Prior

to conducting primary analyses, descriptive analyses will be conducted to examine data distribution, outliers and potentially important covariates for inclusion in multivariate model diagnostics. We will evaluate normality using normal quantile plots and standard tests of normality incorporated in basic statistical packages, including SPSS and SAS.

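### As written, the mediator–outcome association in the mechanism rule screens out little, because ordinary between-person correlation tends to satisfy it

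*Combined protocol and SAP*

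**What the plan says.** Section 11.2.3 sets out an exploratory mechanism analysis. The first part relates participation in the intervention to a composite mediator, Perceived Control Over Pain, and to its four component scales. The second part is the association "2) between mediators and outcomes". Positive correlations on both are to count as evidence of a potential mediating effect. The section does not name the time point, say whether levels or changes are correlated, mention adjustment for arm or baseline, or call for an indirect-effect estimate, a significance level or a size threshold.

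Mediators and outcomes come from the same calls. Section 7.2 says that "participants will complete the validated measures tested as outcomes or mediators listed above", and Section 5.4 provides for "two data collection telephone interviews (at baseline and 8 weeks from baseline"). In the Section 7.1 schedule, "Survey of Pain Attitudes (SOPA) - Control subscale" and the other three component scales are marked at weeks 0 and 8, as is pain interference. There is no mid-program measurement. Global impression of change is marked at week 8 only.

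Section 11.2.2 does adjust for the baseline value of the outcome, but only in the treatment-effect models for primary and secondary outcomes. Section 11.1 adds: "This pilot study is not powered to determine the statistical significance of effects".

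**The concern.** Randomisation protects the arm–mediator association. It does not protect the mediator–outcome association, which is an observational correlation among about 40 people. If people who feel more in control also report less interference before any treatment, that correlation carries into week 8 and can satisfy the second part of the rule without any action of the program.

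The case that matters most is a program that raises perceived control but does not thereby reduce interference. The first association is then genuinely positive, the second is positive for unrelated reasons, and the rule credits a mechanism that is absent. One stated aim of the pilot is to explore mechanisms of effect, so such a reading could carry into the design of a later trial.

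**Working it through.** The documents give no correlation, power or detectable effect for this analysis, so there is no stated figure to reproduce.

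**Inputs from the documents.** The trial is a "randomized (waitlist) pilot trial (n=40"), and "Participants will be randomized to one of two study arms in a 1:1 ratio", so about 20 per arm. Timing: "We will collect outcome data at two time points: baseline and 8 weeks from baseline".

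**Assumptions not in the documents.**
- Baseline mediator–outcome correlation ρ of 0.3 or 0.5.
- Correlation of 0.7 between baseline and week 8 for each measure, with independent follow-up noise and unit variances.
- Both measures scored so that higher is better.
- Week-8 values pooled over arms, no losses, and two-sided 0.05 wherever significance is mentioned.

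**Step 1. Mediator–outcome association, no program effect.** The week-8 correlation is r = 0.7 × 0.7 × ρ = 0.49ρ, which is 0.147 or 0.245. By Fisher's z, P(r > 0) = Φ(atanh(r) × √(n − 3)) with √37 = 6.083.
- ρ = 0.3: Φ(0.148 × 6.083) = Φ(0.90) = 82%.
- ρ = 0.5: Φ(0.250 × 6.083) = Φ(1.52) = 94%.

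The chance of positive and significant is Φ(0.90 − 1.96) = 14% or Φ(1.52 − 1.96) = 33%. Simulation agrees: 82% / 94% positive and about 15% / 34% significant.

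**Step 2. Both associations, no program effect.** The arm–mediator comparison is positive half the time by chance: 0.5 × 0.82 = 41% and 0.5 × 0.94 = 47%. Simulation gives the same, with both significant in under 1%.

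**Step 3. The program moves the mediator by an assumed 0.8 SD, not the outcome.** The standard error of the arm difference is √(2/20) = 0.316, so the first association is positive with probability Φ(0.8/0.316) = Φ(2.53) = 99.4%. Pooled mediator variance rises to 1 + 0.8² × 0.25 = 1.16, so r falls to 0.147/√1.16 = 0.136 or 0.245/√1.16 = 0.227. P(r > 0) becomes Φ(0.84) = 79.8% or Φ(1.41) = 92.1%. Treating the two as nearly independent, both are positive in 0.994 × 0.798 = 79% or 0.994 × 0.921 = 92%. Simulation gives about 80% and 91%, with both significant in about 9% and 19%. There is no mediation in any of these trials.

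**Step 4. Effect of adjustment.** With arm, baseline mediator and baseline outcome in the model, the mediator–outcome association in the same simulated trials is positive in about 50% and positive and significant in about 2%, as it should be when nothing is there.

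**Step 5. What adjustment cannot remove.** A second simulation (1,500 runs per setting, n = 40, no program effect) used a stable between-person component with 70% of the variance and stable correlations of 0.3 / 0.5 / 0.7.

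| Same-call error correlation | Plain week-8 correlation, positive and significant | Adjusted for arm and both baselines |
|---|---|---|
| 0 | 27% / 60% / 92% | 4% / 6% / 9% |
| 0.3 (assumed) | 47% / 84% / 99% | 44% / 51% / 63% |

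Adjustment removes most of the stable between-person part. It does not remove error shared because both measures are reported on one call.

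**The case against.** A reader might infer that the pilot will report evidence for its mechanism whether or not one exists. The documents do not support that. The rule requires both associations, and the first compares randomised arms, so pre-existing correlation cannot bias it. With no program effect at all, the full rule is met in fewer than half of trials on sign alone. About half of that risk is the coin flip in the first association, which comes from using sign without a threshold.

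A reader might also infer that the plan has chosen raw, unadjusted week-8 correlations. It has not; it is silent. Change scores in the Step 1 model would bring the mediator–outcome association down to about 61% / 68% positive. This objection stands in part: the week-8 reading follows the outcome model in Section 11.2.2, but it is a reading.

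Direction also matters. The Section 2 objective is decreased pain interference, so a low score is the good one. A control-type scale would then be expected to correlate negatively with it, and a literal requirement of a positive correlation would fail rather than pass. The point holds only once direction is aligned, which the plan does not do.

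Finally, the analysis is exploratory, its conclusion is worded as potential, and the trial is stated not to be powered. All of that is fair and limits the consequence. It does not make a check that screens out little more informative, and a better one is available from data already scheduled.

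**Conclusion.** The concern holds for the mediator–outcome association and not for the rule as a whole. With aligned scores and week-8 values, that association adds little screening. The rule then rests largely on the sign of the arm–mediator comparison and is most misleading when the program moves perceived control but not interference. The sizes depend on the assumed correlation, stability and 0.8 SD shift, none of which the documents supply. The two simulation models differ noticeably at the same nominal correlation, so the percentages illustrate scale and are not predictions. What is affected is how mechanism findings are read. A worthwhile correction to the SAP text, not a threat to the endpoint analyses.

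**What to change.** In Section 11.2.3:

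1. State the scoring direction of each component scale, the composite and each outcome, and that week-8 values are analysed.
2. For the arm–mediator association, regress week-8 mediator on arm and baseline mediator.
3. For the mediator–outcome association, regress week-8 outcome on week-8 mediator, arm, baseline mediator and, where one exists, baseline outcome. Global impression of change has no baseline value, so use arm and baseline mediator there.
4. Replace the sign rule with the indirect effect (the product of the two coefficients) and a bootstrap interval, presented as exploratory.
5. State that mediator and outcome are reported on the same call, so shared reporting error and temporal order cannot be resolved and the result shows associated change only.

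This costs SAP wording and a few regressions on scales already scheduled. The downside is a few degrees of freedom among about 40 participants and a less favourable exploratory claim.
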